## Statement of Compliance

This study will be conducted in accordance with the Code of Federal Regulations on the Protection of Human Subjects (45 CFR Part 46), 21 CFR Parts 50, 56, 312, and 812 as applicable, any other applicable US government research regulations, and institutional research policies and procedures. The International Conference on Harmonisation ("ICH") Guideline for Good Clinical Practice ("GCP") (sometimes referred to as "ICH-GCP" or "E6") will be applied only to the extent that it is compatible with FDA and DHHS regulations. The Principal Investigator will assure that no deviation from, or changes to the protocol will take place without prior agreement from the sponsor and documented approval from the Institutional Review Board (IRB), except where necessary to eliminate an immediate hazard(s) to the trial participants. All personnel involved in the conduct of this study have completed Human Subjects Protection Training.

CONFIDENTIAL

This material is the property of the NYU School of Medicine and Langone Medical Center. Do not disclose or use except as authorized in writing by the study sponsor

## List of Abbreviations

ACR	Acute Cellular Rejection
AE	Adverse Event/Adverse Experience
AMR	Antibody-mediated Rejection
CFR	Code of Federal Regulations
CKD	Chronic Kidney Disease
CRF	Case Report Form
CSOC	Clinical Study Oversight Committee
DCC	Data Coordinating Center
DHHS	Department of Health and Human Services
DSA	Donor-Specific Antibody
DSMB	Data and Safety Monitoring Board
FFR	Federal Financial Report
FWA	Federalwide Assurance
GCP	Good Clinical Practice
HIPAA	Health Insurance Portability and Accountability Act
ICF	Informed Consent Form
ICH	International Conference on Harmonisation
IR	Immediate Release
IRB	Institutional Review Board
ISM	Independent Safety Monitor
MOP	Manual of Procedures
N	Number (typically refers to participants)
NIH	National Institutes of Health
OHRP	Office for Human Research Protections
OHSR	Office of Human Subjects Research
PI	Principal Investigator
QA	Quality Assurance
QC	Quality Control
SAE	Serious Adverse Event/Serious Adverse Experience
SOP	Standard Operating Procedure
US	United States

CONFIDENTIAL

This material is the property of the NYU School of Medicine and Langone Medical Center. Do not disclose or use except as authorized in writing by the study sponsor

## Protocol Summary

Title	Pilot Study Comparing early conversion to Extended-release Tacrolimus (ENVARSUS XR) to immediate-release Tacrolimus in lung transplant recipients
Short Title	Envarsus XR in Lung Transplant
Brief Summary	Patients undergoing a lung transplant will be enrolled. All patients will undergo lung transplantation with standard post-operative management, including triple immunosuppression. As soon as the patient is deemed appropriate to take medications via the oral route, they will be converted from IR tacrolimus to Envarsus XR. Patients will be followed per site's standard of care.
Phase	Pilot study
Objectives	To determine the feasibility of early conversion to Envarsus XR in patients who receive a lung transplant. To compare the impact of tacrolimus formulation on CKD, ACR, AMR, and de novo DSA within the first year post-lung transplant.
Methodology	Single-center, open-label study
Endpoint	Incidence of CKD, ACR, AMR, and de novo DSA in the first year post-lung transplant
Study Duration	Two years
Participant Duration	One year
Duration of IP administration	One year
Population	Adult patients undergoing lung transplantation
Study Sites	NYU Langone Hospital
Number of participants	Sixty patients (20 patients who received IR tacrolimus and 40 patients who will receive Envarsus XR)
Description of Study Agent/Procedure	Lung transplantation will be performed per standard-of-care techniques. All post-transplant management, including initial triple immunosuppression, will be carried out per standard of care. Once the patient is able to take medications via the oral route, they will be converted to Envarsus XR, which will be maintained for the first year post-lung transplant.
Reference Therapy	IR tacrolimus
Key Procedures	Patients in the Prospective Cohort will receive lung transplantation and post-operative management per standard protocol, including frequency of laboratory assays, surveillance bronchoscopy, and DSA assessment by single-antigen bead assay.
Statistical Analysis	Categorical variables will be compared using chi-square test or Fisher's exact test, as appropriate. Continuous variables will be compared using the Mann-Whitney U test for nonparametric data.

CONFIDENTIAL

This material is the property of the NYU School of Medicine and Langone Medical Center. Do not disclose or use except as authorized in writing by the study sponsor

## Schematic of Study Design

Envarsus XR	ARM 1	n=40	Envarsus XR to be initiated once patient is tolerating oral medications
IR tacrolimus (historical control)	ARM 2	n=20	Historical cohort of patients maintained on IR tacrolimus following transplant

CONFIDENTIAL

This material is the property of the NYU School of Medicine and Langone Medical Center. Do not disclose or use except as authorized in writing by the study sponsor

## 2 Introduction, Background Information and Scientific Rationale

### 2.1 Background Information and Relevant Literature

Lung transplantation remains the definitive cure for many end-stage lung diseases. Despite advances in surgical technique and medical therapy, morbidity and mortality remain unacceptably high. Chronic lung allograft dysfunction (CLAD) is the major barrier to long-term survival in lung transplant recipients. The risk for CLAD is heterogeneous, yet acute cellular rejection (ACR) has consistently been identified as a risk factor for the development of CLAD, with just one episode of A1 ACR portending a higher likelihood of CLAD. Minimizing ACR in the first year post-lung transplant may therefore reduce the incidence of CLAD.

Tacrolimus is the backbone of rejection prevention following lung transplantation. Interpatient variability in tacrolimus pharmacokinetics make achieving consistent systemic exposure challenging and necessitate the use of therapeutic drug monitoring (TDM). Even with TDM, tacrolimus trough levels will vary over time potentially leaving patients at increased risk for ACR.

Tacrolimus trough level variability was first described as a risk for ACR in lung transplant recipients by Chiang and colleagues. They measured trough level variability utilizing the standard deviation (SD). In their cohort, the risk of ACR was increased by 23% for every 1 unit increase in SD within the first 3 months post-transplant. Counterintuitively, the mean tacrolimus trough level was higher in patients who had rejection, and the mean tacrolimus trough level pre-rejection was not predictive of rejection. A similar study retrospectively reviewed 110 lung transplant recipients to evaluate the effect of tacrolimus SD on CLAD. Tacrolimus SD was greatest in the first 6 months post-transplant, but was similar between months 6-12 and 12-24. Again it was observed that for each 1 unit increase in tacrolimus SD the risk of CLAD and death was significantly increased. Recent data in lung transplant recipients found that increasing the time-in-therapeutic range for tacrolimus by 10% within the first year post-transplant reduced the burden of ACR by 54%. Similar data was recently published in heart transplant recipients where patients with high tacrolimus variability had an increased rate of chronic rejection despite similar mean C0 levels. Taken

CONFIDENTIAL

This material is the property of the NYU School of Medicine and Langone Medical Center. Do not disclose or use except as authorized in writing by the study sponsor

together, this data suggests that the tacrolimus trough level in and of itself is not sufficient monitoring to protect against rejection and that trends in trough levels should be monitored as well.

Envarsus XR is a once-daily, extended-release formulation of tacrolimus that utilizes MeltDose technology to optimize the pharmacokinetics of tacrolimus. Pharmacokinetic studies in kidney transplant recipients demonstrated more consistent peak and peak-to-trough levels, decreased Cmax and increased Tmax for Envarsus XR as compared to IR tacrolimus. Additionally, bioavailability was improved with a stronger correlation between trough concentration (C0) and AUC. The randomized, phase III MELT trial was the first to compare the efficacy and safety of IR tacrolimus with conversion to Envarsus XR in kidney transplant recipients. The primary efficacy endpoint was a composite of death, graft failure, biopsy-proven acute rejection (BPAR), or loss to follow-up over a 12 month period. Tacrolimus TDD was decreased by 30% in patients converted to Envarsus XR. There was a significant decrease in TDD with conversion to Envarsus XR despite similar trough levels. The efficacy endpoint was similar between groups (2.5 vs. 2.5%, p>0.999). Additionally, there were no differences between individual components of the composite endpoint. A subsequent prospective, double-blind, double-dummy, multicenter, phase III comparison of IR tacrolimus and de novo Envarsus XR was conducted to demonstrate non-inferiority at 24-months follow-up. Treatment failure defined as death, transplant failure, BPAR, or loss to follow-up was similar between the two drugs (Envarsus XR 23.1%, IR tacrolimus 27.3%) and well below the 10% non-inferiority margin. There was no significant difference in safety outcomes, including changes in estimated glomerular filtration rate (eGFR) and serum creatinine (Scr) was similar between groups. Certain subgroup populations (African-American race, age > 65, female gender) demonstrated trends towards significant efficacy benefit with Envarsus XR, however these groups were too small to reach statistical significance.

A phase II study comparing the pharmacokinetics of Envarsus XR to another unique prolonged-release tacrolimus formulation (Advagraf) is the only published experience to date in lung transplant recipients. This open-label, single-arm, prospective evaluated 20 lung transplant recipients stable on Advagraf who were then converted to Envarsus XR at a conversion dose of 1:0.7. Mean AUC was similar despite significantly lower dosing requirements in the Envarsus XR arm (5.05 vs. 3.36 mg, p=0.00002). Time to peak concentration was prolonged with Envarsus XR compared to Advagraf (325 vs. 125 minutes, p<0.001). Adverse events did not differ between the two formulations over the 6 month follow-up, and no major adverse events were considered related to the tacrolimus formulation or required withdrawal of therapy. It is unknown if Envarsus XR would improve immunologic outcomes in lung transplant recipients by providing a stable pharmacokinetic profile and minimizing variability.

Currently at NYU Langone Health (NYULH), our practice has been to convert lung transplant recipients from IR tacrolimus to Envarsus XR following discharge from the hospital because of our observations of improved adherence and reduced side effects in this population. The only deterrent to inpatient use is the lack of availability on NYULH formulary. We have however experienced subtherapeutic tacrolimus C0 during the outpatient conversion due to the inability to measure frequent C0 concentrations. Early conversion to Envarsus XR in the hospital would allow for daily monitoring of C0 levels and appropriate dose adjustments to be made leading to stable Envarsus XR dosing and potentially minimizing the risk of rejection during the early post-transplant period.

## **2.2 Name and Description of the Investigational Agent**

Envarsus XR (tacrolimus extended-release tablets)  
Manufactured by Rottendorf Pharma GmbH, North Rhine-Westphalia, Germany  
Manufactured for Veloxis Pharmaceuticals, Cary, NC

Envarsus XR is an FDA-approved drug for the prophylaxis of organ rejection in de novo kidney transplant patients or in kidney transplant patients converted from IR tacrolimus when used with other immunosuppressants.

Envarsus XR is a novel extended-release formulation of tacrolimus created using MeltDose technology.

CONFIDENTIAL

This material is the property of the NYU School of Medicine and Langone Medical Center. Do not disclose or use except as authorized in writing by the study sponsor

## 2.2.1

### Preclinical Data

Compared to IR tacrolimus, Envarsus XR has improved bioavailability, a lower peak concentration ( $C_{max}$ ), similar area-under-the-concentration-time curve (AUC) despite lower total daily dosing (TDD).

## 2.2.2

### Clinical Data to Date

A phase II study comparing the pharmacokinetics of Envarsus XR to another unique prolonged-release tacrolimus formulation (Advagraf) is the only experience to date in lung transplant recipients. This open-label, single-arm, prospective evaluated 20 lung transplant recipients stable on Advagraf who were then converted to Envarsus XR at a conversion dose of 1:0.7. Mean AUC was similar despite significantly lower dosing requirements in the Envarsus XR arm (5.05 vs. 3.36 mg,  $p=0.00002$ ). Time to peak concentration was prolonged with Envarsus XR compared to Advagraf (325 vs. 125 minutes,  $p<0.001$ ).

The randomized, phase III MELT trial was the first to compare the efficacy and safety of IR tacrolimus with conversion to Envarsus XR in kidney transplant recipients. The primary efficacy endpoint was a composite of death, graft failure, biopsy-proven acute rejection (BPAR), or loss to follow-up over a 12 month period. Tacrolimus TDD was decreased by 30% in patients converted to Envarsus XR. There was a significant decrease in TDD with conversion to Envarsus XR despite similar trough levels. The efficacy endpoint was similar between groups (2.5 vs. 2.5%,  $p>0.999$ ). Additionally, there were no differences between individual components of the composite endpoint. A subsequent prospective, double-blind, double-dummy, multicenter, phase III comparison of IR tacrolimus and *de novo* Envarsus XR was conducted to demonstrate non-inferiority at 24-months follow-up. Treatment failure defined as death, transplant failure, BPAR, or loss to follow-up was similar between the two drugs (Envarsus XR 23.1%, IR tacrolimus 27.3%) and well below the 10% non-inferiority margin. There was no significant difference in safety outcomes, including changes in estimated glomerular filtration rate (eGFR) and serum creatinine (Scr) was similar between groups. Certain subgroup populations (African-American race, age > 65, female gender) demonstrated trends towards significant efficacy benefit with Envarsus XR, however these groups were too small reach statistical significance.

A phase IIIb prospective study compared continuation of IR tacrolimus to Envarsus XR conversion in patients on IR tacrolimus with significant tremor. Improvement in tremor with conversion to Envarsus XR was documented by two separate clinical scoring systems and by patient-reported quality-of-life (78.9% reported improvement with conversion).

## 2.2.3

### Dose Rationale (if applicable)

Dosing will be converted on an individual basis. Because all patients will be initiated on IR tacrolimus via the sublingual or enteral route, conversion will be dependent on several factors: tacrolimus TDD, tacrolimus trough level, and patient clinical status (i.e. infection, rejection, acute kidney injury, etc.). Envarsus XR conversion dose will be decided upon by the attending pulmonologist and the clinical pharmacotherapy specialist caring for the patient, who are also members of the study team.

## 2.3 Rationale

Tacrolimus is the primary immunosuppressant medication administered following lung transplant. Despite its widespread use, tacrolimus is limited by inconsistent pharmacokinetics (PK), variability in systemic exposure, difficulties with therapeutic drug monitoring, concentration-related neurologic side effects, and poor patient adherence. Envarsus XR is a once-daily, extended-release formulation of tacrolimus that utilizes MeltDose technology to optimize the pharmacokinetics of tacrolimus. Phase II studies in kidney transplant recipients demonstrated more consistent peak and peak-to-trough levels for Envarsus XR as compared to IR tacrolimus. Additionally, bioavailability was improved to 30% from 17% with a stronger correlation between trough concentration ( $C_0$ ) and AUC.

Recent data in lung transplant recipients found that increasing the time-in-therapeutic range for tacrolimus by 10% within the first year post-transplant reduced the burden of ACR by 54%. Similar data was recently published in heart transplant recipients where patients with high tacrolimus variability had an increased rate of chronic rejection despite similar mean  $C_0$  levels. Taken together, these data highlight the clinical

CONFIDENTIAL

This material is the property of the NYU School of Medicine and Langone Medical Center. Do not disclose or use except as authorized in writing by the study sponsor

consequences of inconsistency in systemic exposure to tacrolimus. Envarsus XR may improve immunologic outcomes in lung transplant recipients by providing a stable pharmacokinetic profile and minimizing variability.

## 2.4 Potential Risks & Benefits

### 2.4.1

### Known Potential Risks

There is likely to be no potential risk to the patient as Envarsus XR has been shown to produce equivalent outcomes to IR tacrolimus in stable kidney transplant recipients. Adverse effects have similarly been equivocal or typically improved compared to IR tacrolimus. This study involves minimal to no risk to individual patients as it is a retrospective review of medical records and will involve collection and storage of de-identified patient data only.

### 2.4.2

### Known Potential Benefits

The potential benefits of this study include improved adherence and convenience of maintenance immunosuppressive therapy, reduction in neurologic adverse effects (e.g. tremor) as demonstrated in the STRATO trial, and a decrease in the burden of ACR within the first-year post-transplant. There is no direct benefit to the historical control cohort.

## 3 Objectives and Purpose

### 3.1 Primary Objective

The primary objective will be to assess the feasibility of early conversion to Envarsus XR at 1-year follow-up.

### 3.2 Secondary Objectives (if applicable)

Secondary objectives will be to assess immunologic outcomes that may be impacted by conversion to Envarsus XR and potential mitigation of concentration-related side effects.

## 4 Study Design and Endpoints

### 4.1 Description of Study Design

This study will be a prospective, open-label, non-randomized, parallel arm, single-center trial comparing new lung transplant recipients converted to Envarsus XR to a historical cohort of patients who received IR tacrolimus.

### 4.2 Study Endpoints

#### 4.2.1

#### Primary Study Endpoints

The primary endpoint will be percentage of patients remaining on Envarsus XR at 1-year follow-up.

#### 4.2.2

#### Secondary Study Endpoints

Secondary endpoints will include freedom from ACR at 1-year follow-up, ACR burden at 1-year follow-up as assessed by the composite rejection standardized score (CRSS), treated episodes of rejection, the incidence of chronic lung allograft dysfunction (CLAD) at 1-year, incidence of de novo DSA in the first postoperative year, change in estimated glomerular filtration rate (eGFR) over the first post-operative year, and 1-year survival.

CONFIDENTIAL

This material is the property of the NYU School of Medicine and Langone Medical Center. Do not disclose or use except as authorized in writing by the study sponsor

## 5 Study Enrollment and Withdrawal

### 5.1 Inclusion Criteria

In order to be eligible to participate in this study, an individual must meet all of the following criteria:

**Prospective arm:**

1. Age  $\geq$  18 years
2. Received a lung or heart-lung transplant at NYU Langone Health
3. Be able to convert to Envarsus XR within the first month post-transplant
4. Able and willing to provide informed consent

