**Historical control:**

1. Age  $\geq$  18 years
2. Received a lung or heart-lung transplant at NYU Langone Health
3. Completed one year from transplant on IR tacrolimus

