#### **6.1.5 Dosing and Administration**

The dose of Envarsus XR is administered once daily, most commonly prior to the morning meal. The precise dose will be determined by TDM of tacrolimus C0 levels with dose adjustments to achieve the goal prescribed by the transplant pulmonologist. The dose can include any combination of the 0.75, 1 and 4 mg tablets. The tablet should be swallowed whole, and should not be split, chewed or crushed.

CONFIDENTIAL

This material is the property of the NYU School of Medicine and Langone Medical Center. Do not disclose or use except as authorized in writing by the study sponsor

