## **10.3 Analysis Datasets**

All subjects will be entered into a database containing de-identified information. All patients who take one dose of the study drug will be included in the safety analyses (intention-to-treat). However, only patients completing the full first year post-lung transplant will be included in the efficacy analysis (per-protocol analysis).

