#### **10.5 Sample Size**

We plan to prospectively enroll 40 patients into the Envarsus XR arm to provide a 2:1 sample size with a historical control of patients who received IR tacrolimus. The sample size of 40 patients for the Prospective Cohort was chosen based on the expected number of lung transplants performed in one year at NYULH. The Historical Control Cohort sample size includes all patients who were transplanted at NYULH and completed one year of follow-up post lung transplant while maintained on IR tacrolimus. The 2:1 sample size was chosen as the purpose of the study is to gain experience with Envarsus XR in lung transplant recipients and IR tacrolimus has many years of clinical use. As this is a pilot study, there will be no power calculations.

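### The two cohorts enter on different conditions: month-1 convertibility for Envarsus XR and one-year completion on IR tacrolimus for controls. The secondary comparisons do not align them on early recovery.

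*Combined protocol and SAP*

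**What the plan says.** Section 5.1 gives each cohort its own entry conditions.

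- **Envarsus XR arm, criterion 3:** "Be able to convert to Envarsus XR within the first month post-transplant". Section 14.1 and the Schedule of Events (Section 20, screening on POD 0 to 30) confirm a 30-day window.
- **Historical control, criterion 3:** "Completed one year from transplant on IR tacrolimus". Section 10.5 repeats this, taking all NYULH recipients who "completed one year of follow-up post lung transplant while maintained on IR tacrolimus". Neither place sets a condition at month 1.

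Two other passages show what criterion 3 selects on. Section 2.2.3 says that "all patients will be initiated on IR tacrolimus via the sublingual or enteral route". Section 6.1.5 says of Envarsus XR: "The tablet should be swallowed whole, and should not be split, chewed or crushed". Conversion therefore requires moving to whole oral tablets within the month.

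Section 10.3 restricts the efficacy analysis to patients who complete the first post-transplant year. Section 10.4.3 compares the cohorts on ACR, CRSS, treated rejection, CLAD, de novo DSA and mortality, and Section 10.4.4 adds kidney function. No covariates are named for the logistic or linear regressions. Section 10.4.6 compares baseline items, including ventilation, ECMO and lung allocation score, by chi-square test to look for imbalance. It states no matching or adjustment. The primary endpoint (Sections 4.2.1 and 10.4.2) is the percentage still on Envarsus XR at one year, described in that arm alone.

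**The concern.** Early recovery plausibly predicts later outcome, and the two cohorts are selected on it differently. Take a recipient who is ventilated and tube-fed for six weeks and then completes the year on IR tacrolimus. That person cannot enter the Envarsus XR arm, yet qualifies as a control. If such recipients have more rejection, CLAD or DSA, or lose more kidney function, the control results worsen for a reason unrelated to formulation.

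The comparison matters to this protocol. The Protocol Summary sets out to compare the effect of formulation on CKD, ACR, AMR and de novo DSA, and Section 10.2 states a hypothesis about ACR. The safeguard in Section 10.4.6 is weak. An imbalance test with 20 controls can miss a real difference, and the listed items do not include the selecting variable itself, which is oral intake by about day 30.

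**Working it through.** The plan's own figures agree: 40 + 20 = 60 and 40/20 = 2. It gives no power, event rate or effect size, so there is no planned calculation to reproduce. The check below asks how far the entry rules alone could move the ACR comparison when the drug has **no effect**.

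**Assumed inputs (none is in the documents).** One-year ACR risk in fast recoverers: 30%. Share s of slow recoverers (unable to convert in month 1): 10% to 30%. Relative ACR risk RR of slow versus fast recoverers: 0.8 to 2.0. Positive values favour Envarsus XR.

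**Step 1: the month-1 condition alone.** Bias = s × 30% × (RR − 1).

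| RR | s = 10% | s = 30% |
|---|---|---|
| 0.8 | −0.6 points | −1.8 points |
| 1.0 | 0 | 0 |
| 1.5 | +1.5 points | +4.5 points |
| 2.0 | +3.0 points | +9.0 points |

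For eGFR the bias is s × d, where d is the extra loss in slow recoverers. With d assumed at 0 to 15 mL/min, it runs from 0 to 0.30 × 15 = 4.5 mL/min.

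**Step 2: add the controls' one-year rule.** Let c_s and c_f be the one-year completion rates in slow and fast recoverers, and k the ACR risk of non-completers relative to completers. Three pairs (c_s, c_f) were tried: (90%, 90%), (50%, 85%) and (30%, 80%). RR ran from 1.2 to 2.0 and k from 1 to 2.

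- Slow share among controls: w = s·c_s / [s·c_s + (1 − s)·c_f].
- Risk in fast completers: 0.30 / [c_f + (1 − c_f)k].
- Risk in slow completers: 0.30·RR / [c_s + (1 − c_s)k].
- Control risk: w × slow-completer risk + (1 − w) × fast-completer risk.

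The one-year rule thins out slow recoverers. At s = 20%, w is 0.10/0.78 = 12.8% for the second pair and 0.06/0.70 = 8.6% for the third.

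- *Lowest case* (s = 30%, third pair, RR = 1.2, k = 2): w = 0.09/0.65 = 13.8%. Fast-completer risk = 0.30/1.2 = 25.0%. Slow-completer risk = 0.36/1.7 = 21.2%. Control risk = 0.138 × 21.2 + 0.862 × 25.0 = 24.5%. Against Envarsus XR completers (25.0%) the bias is −0.5 points. Against all dosed Envarsus XR patients (30%) it is −5.5 points.
- *Highest case* (s = 30%, first pair, RR = 2, k = 1): control risk = 0.3 × 60 + 0.7 × 30 = 39%. Against 30% the bias is +9.0 points on either basis.

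The net range is therefore **−0.5 to +9.0 points in the completer set** and −5.5 to +9.0 points if all dosed patients are analysed.

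**Step 3: effect on the test.** Exact enumeration of the two-sided Fisher test at 20 versus 40 gives 3.6% rejections with both risks at 30%, and 9.2% with 39% versus 30%. For scale, the standard error of the difference at 30% risk is √(0.21/20 + 0.21/40) = 12.5 points.

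**Step 4: survival.** Controls have no first-year deaths by construction. If all dosed Envarsus XR patients were counted and mortality were 5%, the chance of at least one death in 40 would be 1 − 0.95^40 = 87%, which is a bias against Envarsus XR. In the completer set neither cohort can have a death, and the comparison carries no information.

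**The case against.** The strongest reply is that controls carry a severe restriction of their own. Recipients who died in year 1 or left IR tacrolimus are in neither cohort, so the slow recoverers among controls are those who came through the year. From criterion 3 a reader might infer that the comparison as a whole favours Envarsus XR. The documents do not support that. They do not say that slow recovery raises ACR risk, the net sign in Step 2 is not fixed, and one-year survival is governed by the completion rules instead. This part of the objection stands.

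It does not remove the point. Section 10.3 requires first-year completion for the efficacy analysis, so that condition is largely mirrored in the Envarsus XR arm. The month-1 condition is mirrored nowhere. The −5.5 bound needs an all-dosed efficacy analysis, which Section 10.3 does not plan.

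It is also fair to say that criterion 3 follows from the purpose of studying early conversion, that the study is an unpowered pilot, and that the possible bias is smaller than the sampling error. These limit the weight of the point. They are no reason to leave the selecting variable unrecorded.

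A reader might further infer from Section 2.1, which describes conversion after discharge as current practice, that controls are enriched for patients who could not convert. The documents give no calendar dates for the control cohort, so this remains only a possibility.

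**Conclusion.** The entry conditions are not equivalent, and nothing in Section 10.4 aligns the cohorts on month-1 recovery. In the completer set this can favour Envarsus XR on the secondary rejection, CLAD, DSA and kidney comparisons, provided that slow recovery raises risk. On the assumptions above, the net ACR bias is between −0.5 and +9.0 points. With no excess risk the month-1 condition contributes nothing, and with lower risk it reverses slightly.

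The true size is unknown, and the net direction also depends on the one-year-completion rule. The finding does not touch the primary endpoint and draws no support from one-year survival. It is worth correcting because the correction is cheap and will show the direction and size in the trial's own data.

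**What to change.** 1. Add one item to the retrospective data in Section 7.2.2: whether each control was receiving tacrolimus orally, not sublingually or by tube, by day 30 after transplant, taken from the medication administration record.
2. In Section 10.3, define a landmark-matched control set as the controls meeting that item. Keep the others as a listed group.
3. In Sections 10.4.3 and 10.4.4, commit in advance to reporting every between-cohort comparison twice in the completer set: against the matched controls and against all controls.
4. State two limitations. The route used is only a proxy for the ability to swallow tablets. The one-year-completion rule remains a separate selection that this change does not remove.

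A requirement to be alive at day 30 is unnecessary, because one-year completion already implies it.

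The cost is one chart item for each of 20 controls and a second column in the tables. No participant is affected. The downside is precision: if 10% to 30% of controls fail the landmark, the matched set is 14 to 18 patients, which is why the full set is also shown.
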